**b) STUDY POPULATION**

The target population for the pilot trial and the eventual full trial will be patients with elevated symptoms of depression, anxiety, post-traumatic stress, and/or substance use, who are also at risk for suboptimal HIV care engagement. 60 participants will be enrolled.

Inclusion Criteria

1. Age  $\geq$  18 years.
2. Patient receiving HIV care at UAB 1917 Clinic.
3. Elevated symptoms of depression, anxiety, post-traumatic stress, or substance use disorder: At least one of the following:
  - i. Patient Health Questionnaire-9 score  $\geq$  10;
  - ii. Generalized Anxiety Disorder 7-Item Scale score  $\geq$  10;
  - iii. Post-Traumatic Stress Symptoms Checklist for DSM-5 score  $\geq$  33;
  - iv. ASSIST score  $\geq$  11 for alcohol or  $\geq$  4 for any other substance
4. At risk for suboptimal HIV care engagement: At least one of the following:

- i. Engaged in HIV care for the first time within the past 6 months;
- ii. Have an HIV RNA viral load >1,000 copies/mL within the past 6 months;
- iii. . Antiretroviral regimen was changed due to treatment failure within the past 6 months;
- iv. No-showed to an HIV primary care appointment within the past year.

5. Willing to provide written informed consent.

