*HIV-related outcomes* (the primary outcomes for the eventual full-scale trial) will be defined as (a) suppressed HIV RNA viral load at 4 and 9 months and (b) HIV appointment adherence between baseline and 12 months. Viral load will be captured from clinical records when possible; if no viral load is scheduled at the requisite time point for the study, then the study will order and pay for a viral load test. Suppressed viral load will be defined as a value <200 copies/mL. HIV appointment attendance will be defined using the HRSA attendance measure (primary) and the kept-visit proportion (secondary). *Mental health outcomes* (the secondary outcomes for the eventual full-scale trial) will be defined as depressive, anxiety, post-traumatic stress, and substance use symptom severity measured at 4 months and 9 months. Depressive symptom severity will be measured using the Patient Health Questionnaire-9 (PHQ-9), anxiety symptom severity by the GAD-7, post-traumatic stress symptoms by the PTSD Checklist for DSM-5 (PCL-5), and substance use using the Alcohol, Smoking and Substance Involvement Screening Test (ASSIST). We will consider both the simple severity level at follow-up as well as the percentage reduction in symptoms from baseline. We will also create a measure of global symptom improvement which will be the average of the percentage reduction in symptoms from baseline across all of the domains which were elevated at baseline (which could be 1-4 domains depending on the participant's initial presentation).

Assessments will be conducted 4 and 9 months after study enrollment. Participants will receive up to 3 reminder calls at about a week and 48 hours prior to the next outcome assessment.

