## **V. DATA ANALYSIS**

Analyses of primary feasibility, acceptability, and fidelity outcomes will focus on reporting summary statistics with confidence intervals. Analyses of secondary health outcomes will be intent-to-treat analyses between arms comparing each of the secondary outcomes using a generalized linear regression model with link and error distribution appropriate for the specific outcome (i.e., log link and binomial error distribution for binary outcomes; identity link and normal error distribution for continuous outcomes). Intent-to-treat results will be reported as risk or mean differences with two-sided confidence intervals and P values, setting the Type I error probability to 5%.

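### The study-paid viral load is triggered by nothing being scheduled, not by having no result, so a missed scheduled test is uncovered and no missing-data rule supports the intent-to-treat label

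*Combined protocol and SAP*

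**What the plan says.** The Assessments section defines suppression at 4 and 9 months after baseline. On the source of the data it says "Viral load will be captured from clinical records when possible". The one stated back-up, a study-funded test, is conditional: "if no viral load is scheduled at the requisite time point for the study, then the study will order and pay". The cut-off is given as "Suppressed viral load will be defined as a value <200 copies/mL". The section sets no window around either time point and does not say what happens when a test was scheduled but not done.

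Section V (Data Analysis) says: "Analyses of secondary health outcomes will be intent-to-treat analyses between arms comparing each of the secondary outcomes using a generalized linear regression model". Binary outcomes get a log link with binomial error. The section names no analysis set, no method for missing outcomes and no sensitivity analysis.

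Three other places bear on the point:

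- In section b) (Study Population), "No-showed to an HIV primary care appointment within the past year" is one of four alternative ways to meet the risk criterion.
- Section h) (Tracking of Study Patients) has logs for the window and status of outcome assessments, but gives no width for the window.
- Reminder calls (Assessments) and a $50 payment (section j) support attendance at the 4- and 9-month assessments. Nothing ties the blood draw to those assessments.

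**The concern.** A back-up test is useful when the clinic produces no result. As worded, it is ordered when the clinic has no test planned. The two conditions differ for a patient who has a clinic test booked and does not attend. That patient is also the one for whom the outcome is most plausibly informative.

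Missing results could differ by arm. Section a) adds a session on adherence and care engagement to CETA, and appointment attendance is itself a secondary outcome. CETA participants have 7 to 13 weekly in-person sessions (section e), while section f) gives the comparison group no additional treatment. The trial therefore hopes to change the behaviour that generates clinic viral loads.

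If more usual-care than CETA patients lack a result, and those without one are less often suppressed, an analysis of available results flatters usual care. Viral suppression is a planned primary outcome of the full-scale trial, and the Objectives section says the pilot is to guide that trial's design. A distorted pilot estimate could therefore carry forward.

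**Working it through.** **Step 1: apply the rule case by case.**

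- No clinic test scheduled: the study orders one.
- Clinic test scheduled and done: the result comes from the record.
- Clinic test scheduled and missed: no rule is stated.

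**Step 2: follow the third case into the analysis.** A generalized linear model takes its likelihood from participants with an observed outcome. Without imputation or a category for missing values, the uncovered participant contributes nothing. Section V states neither, so exclusion is the default result of its silence.

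**Step 3: illustrate the size.** The plan has no figure to reproduce, since it gives no suppression rate, missingness rate or sample-size derivation. From the documents: 60 participants at 1:1, so about 30 per arm. By assumption: true suppression p = 0.70 in both arms (no effect); suppression among those without a result q = 0.30 to 0.50; share without a result m = 0.10 in CETA and 0.25 in usual care.

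Suppression among those with a result is (p - m×q)/(1 - m).

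| q | CETA, m = 0.10 | Usual care, m = 0.25 | Risk difference (points) |
|---|---|---|---|
| 0.30 | 0.670/0.90 = 0.744 | 0.625/0.75 = 0.833 | -8.9 |
| 0.40 | 0.660/0.90 = 0.733 | 0.600/0.75 = 0.800 | -6.7 |
| 0.50 | 0.650/0.90 = 0.722 | 0.575/0.75 = 0.767 | -4.4 |

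**Step 4: vary the assumptions.**

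- 10% versus 20% missing: usual care becomes 0.800, 0.775 and 0.750, and the difference runs from -5.6 to -2.8 points.
- 20% missing in both arms: the difference is 0, but both arms show 75% to 80% suppressed instead of 70%.
- The 10% and 25% exchanged between arms: the sign reverses, to +4.4 to +8.9 points.
- q = p: no bias at any m.

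**Step 5: a second parameterisation, with a true effect.** Let true suppression be 60% in usual care and 80% in CETA. Let 10% of suppressed patients be missing in both arms, and 40% (usual care) versus 10% (CETA) of unsuppressed patients.

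- Usual care: 0.60×0.90/(0.60×0.90 + 0.40×0.60) = 0.54/0.78 = 0.692.
- CETA: 0.80×0.90/(0.80×0.90 + 0.20×0.90) = 0.72/0.90 = 0.800.

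The estimate is 10.8 points where the truth is 20.

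**Step 6: test the obvious alternative rule.** Counting missing as not suppressed gives p - m×q. With the Step 3 inputs, CETA has 0.670, 0.660 and 0.650, and usual care 0.625, 0.600 and 0.575. The difference is +4.5 to +7.5 points when the truth is zero. This rule is biased too, towards the better-retained arm.

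**The case against.** The strongest reply is that a missed test need not become a missing outcome. After a missed visit nothing may remain scheduled, so the back-up could be read as applying. A rescheduled test or another clinic result might also supply the value. The logs, reminder calls and payments all help. This stands as a reason to expect fewer missing values, but it does not close the gap: the text leaves the case to interpretation, and no window says which later result counts.

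A reader might infer that the plan prescribes an analysis of only those with data. It does not; section V is silent, and its label can be read as analysis by assigned arm whatever the session attendance. Exclusion is what the named model does by default.

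A reader might also infer that missed tests are certain because no-shows are an entry criterion. A no-show is one of four alternatives, and one in the past year does not establish a missing result at month 4 or 9.

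Nor do the documents support a claim of material loss of precision. With 30 per arm and p = 0.70, the 95% half-width is 1.96×√(2×0.70×0.30/30) = 23.2 points. With 27 and 22.5 patients at the Step 3 proportions it is about 22.5 (q = 0.30) to 24.3 (q = 0.50).

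Finally, the stakes are modest. These are secondary, preliminary outcomes of a pilot whose primary outcomes are feasibility, acceptability and fidelity, and a shift of 4 to 9 points lies well inside that half-width. That limits the severity, but a systematic shift is worth preventing when prevention is cheap.

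**Conclusion.** The point holds as a gap in a stated rule: the back-up test does not clearly reach a participant who misses a scheduled one, and section V does not say how the resulting missing outcome is handled.

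Under the Step 3 assumptions the available-case risk difference would be about -4 to -9 points with no true effect. Every rate behind that range is assumed. It would be tempting to conclude that better retention will make CETA look worse. The documents do not support that: the bias vanishes with equal missingness under no true effect, and reverses if CETA has the more missing results. What they do support is that missingness may plausibly differ by arm, because the intervention aims at care engagement and contact is unequal.

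The defect in the trigger concerns viral load only. It is not a reason to change the model for the symptom scales.

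**What to change.** In the Assessments section, replace the trigger with: *if no viral-load result exists within the assessment window tracked in the study log, the study orders and pays for one, tied to the 4- or 9-month assessment.* State the width of that window.

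In section V, state that viral suppression is analysed in all randomised participants, with missing results imputed from arm, the other visit's result and any earlier viral load available in clinic records. The plan does not specify a baseline viral load for everyone, so the imputation should not depend on one. Add sensitivity analyses that include counting missing as not suppressed, with a note that this rule can itself favour the better-retained arm, and report the number missing by arm and visit.

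The cost is a few sentences, a few more tests of a kind the study already funds, and slightly more analysis. The changed trigger matters most, since it reduces the missing data that the analysis must otherwise make assumptions about.

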## **RETENTION PROCEDURES**

However, consistent with standard clinical practice at UAB, participants will be eligible for gas vouchers or bus tickets to facilitate counseling session attendance.

**g) FIDELITY AND SUPERVISION**

Supervision will take place weekly, led by [name]. Supervision will include a brief review of all sessions held since the last supervision as well as detailed discussion and feedback on at least one audio-recorded session per week. Sessions will be audio recorded with clients' permission and will be shared via a secure shared drive. Remote supervision will be facilitated by use of the Evidence-Based Practices Toolkit ([www.ebptoolkit.com](http://www.ebptoolkit.com)), a secure web-based platform that allows tracking and supervision of a growing number of evidence-based interventions; CETA has been built into the EBP Toolkit already. Counselors log each session including key metrics (symptom severity scores), and supervisors and counselors can then review cases together.

Fidelity monitoring will include methods successfully used in previous CETA RCTs. Both clinician adherence (completion of required treatment components) and competence (degree of skill) in delivering CETA will be monitored and systematically rated by [name]. [name] will review clinician documentation of sessions through the EBP Toolkit to monitor adherence and observe a subset of recorded CETA sessions representing the full range of CETA components to rate both clinician adherence and competence. Any observations of low adherence or competence will result in additional clinician training. [name] will also review cases with clinicians and provide feedback on adherence and competence during weekly supervision.

**h) TRACKING OF STUDY PATIENTS**

Study staff will use Qualtrics to capture baseline, 4 and 9 month assessments, as well as viral loads, CETA therapy attendance, HIV care and mental health visits. Study staff will use excel logs to capture prescreening, enrollment, randomization, timeline/window of outcome assessments, status of assessments, reminder call status for assessments. All study staff will be trained in Human Subjects Protections, and this data will be handled in accordance with UAB electronic storage and data transfer guidelines.

The program manager at the University of North Carolina-Chapel Hill will provide oversight of data quality and will conduct monthly audits.

**i) MANAGEMENT AND INTEGRATION OF UAB AND UCSD SITES**

Study PI [name] will conduct regular video conference communication with the UAB staff. Additionally, there will be monthly study team meetings with staff across UAB, UNC-Chapel Hill, Harvard, and the University of Washington. The purpose of these weekly meetings will be to track progress with study milestones, troubleshoot issues that may arise, and discuss any adverse events.

**j) SUMMARY OF COMPENSATION**

**Intervention and Control groups**

|                                       |           |
|---------------------------------------|-----------|
| Screening/Enrollment (Baseline) visit | \$50      |
| 4, and 9 month assessments            | \$50 each |

Participants in the CETA arm will not receive compensation for attending CETA counseling sessions, but will be eligible for gas vouchers or bus tickets to facilitate attendance at counseling sessions, as is standard practice at UAB for all patients.

**IV. DATA COLLECTION AND MANAGEMENT**

All study documentation will be kept in locked file cabinets in in study personnel's offices at UAB. The Qualtrics database can only be accessed by TRACE personnel using UAB and UNC-Chapel Hill computers or encrypted laptops.

## **V. DATA ANALYSIS**

Analyses of primary feasibility, acceptability, and fidelity outcomes will focus on reporting summary statistics with confidence intervals. Analyses of secondary health outcomes will be intent-to-treat analyses between arms comparing each of the secondary outcomes using a generalized linear regression model with link and error distribution appropriate for the specific outcome (i.e., log link and binomial error distribution for binary outcomes; identity link and normal error distribution for continuous outcomes). Intent-to-treat results will be reported as risk or mean differences with two-sided confidence intervals and P values, setting the Type I error probability to 5%.

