**d) SCREENING AND ENROLLMENT**

The Screening and Enrollment Visit will be scheduled based on the patient and research staff's availability and be recorded on a Screening and Enrollment Visit log. Participants will receive a reminder call at about a week and 48 hours prior to the scheduled screening and enrollment visit. The following scales will be administered to the patient to confirm eligibility. If symptoms are elevated in any one of the following, proceed to do the verbal informed consent and complete the baseline questionnaire. If the participant isn't eligible, thank them for their time and pay them \$25.

- a. Depression: PHQ-9
- b. Anxiety: GAD-7
- c. PTS: Trauma Questionnaire + PCL-5
- d. Alcohol/Drugs: WHO ASSIST

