### ***Baseline Assessment***

If a participant is ineligible based on screening assessment, they will be given a \$25 incentive and thanked for their time, and they will not be considered to have been enrolled in the study at any point. If a participant is eligible, the baseline assessment will then be completed. Completion of Baseline assessment will be recorded in excel logs.

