### **Assessments**

| Type      | Name                           | Time Frame                               | Description  |
|-----------|--------------------------------|--|--|
| Primary   | Feasibility of recruitment     | Duration of recruitment phase (9 months) | Number of patients approached in order to accrue the final sample  |
| Primary   | Client acceptability           | 9 months post-baseline                   | Client Satisfaction Questionnaire-8  |
| Primary   | Fidelity                       | At end of study                          | Supervisor rating of each counselor's overall fidelity to each core component that the counselor routinely employed, averaged into a single overall fidelity score |
| Secondary | Suppressed HIV RNA viral load  | 4 months post-baseline                   | HIV RNA viral load <200 copies/mL  |
| Secondary | Suppressed HIV RNA viral load  | 9 months post-baseline                   | HIV RNA viral load <200 copies/mL  |
| Secondary | HIV appointment attendance     | From baseline to 12 months post-baseline | Kept visit proportion: Total number of kept visits divided by total number of missed plus kept visits  |
| Secondary | Depressive symptoms            | 4 months post-baseline                   | PHQ-9  |
| Secondary | Anxiety symptoms               | 4 months post-baseline                   | GAD-7  |
| Secondary | Post-traumatic stress symptoms | 4 months post-baseline                   | PCL-5  |
| Secondary | Substance use symptoms         | 4 months post-baseline                   | ASSIST   |

The **primary outcomes** of the pilot trial will be the feasibility, acceptability, and fidelity of delivery of the adapted CETA protocol. **Secondary outcomes** will include preliminary indicators of impact of the adapted CETA protocol in improving HIV-related

outcomes (eventual R01 primary outcomes) and mental health outcomes (eventual R01 secondary outcomes).

*Feasibility* will be evaluated by examining the recruitment rate (number of patients approached in order to accrue the final sample), reasons for non-participation, proportion of CETA sessions attended, reasons for non-attendance, and total counselor time per session and per patient including preparation, documentation, and supervision.

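### The follow-up symptom severity models name no baseline covariate, although the same four scales are scored at entry: a valid comparison that leaves available precision unused (lowest severity).

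*Combined protocol and SAP*

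**What the plan says.** Section V (Data Analysis) is the whole analysis plan for the secondary outcomes: "Analyses of secondary health outcomes will be intent-to-treat analyses between arms comparing each of the secondary outcomes using a generalized linear regression model". For continuous outcomes it specifies an identity link and normal error, so each symptom score is analysed by ordinary linear regression on arm. No covariate is named there or elsewhere.

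The Assessments table lists the four symptom scales at 4 months, for example "Post-traumatic stress symptoms | 4 months post-baseline". The text after the table adds 9 months and describes two versions of each outcome: "We will consider both the simple severity level at follow-up as well as the percentage reduction in symptoms from baseline". It also defines a global measure that averages percentage reductions over the domains elevated at baseline.

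The same scales are given at entry. Section d (Screening and Enrollment) lists PHQ-9, GAD-7, PCL-5 (with a trauma questionnaire) and WHO ASSIST, and continues: "If symptoms are elevated in any one of the following, proceed to do the verbal informed consent and complete the baseline questionnaire". The Baseline Assessment paragraph says: "If a participant is eligible, the baseline assessment will then be completed". Section h (Tracking of Study Patients) records it: "Study staff will use Qualtrics to capture baseline, 4 and 9 month assessments". The Randomization paragraph comes next after Baseline Assessment; it gives a 1:1 ratio and mentions no stratification.

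**The concern.** In a randomised comparison of a score measured at entry and again at follow-up, the entry score is usually the most useful covariate. It removes the part of the follow-up variation that participants brought with them. Without it, that variation stays in the error term, and any chance difference between arms at entry carries through to the estimate in proportion to the correlation. With 30 per arm, the standard deviation of that chance difference is sqrt(2/30) = 0.26 baseline SDs.

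At stake are the width of the intervals for the symptom differences and whether the choice of model is fixed before the data are seen. The protocol says the secondary outcomes "will include preliminary indicators of impact of the adapted CETA protocol in improving" HIV-related and mental health outcomes, and the Objectives say the pilot should inform the design of a full-scale trial. Feasibility, acceptability and fidelity, which are the pilot's primary outcomes, are not touched. No claim is made about viral suppression.

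**Working it through.** The plan states no power, precision, SD or effect size, so there is no figure of its own to reproduce.

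**Inputs from the documents.** 60 participants (section b); 1:1 allocation, hence 30 per arm (Randomization); two-sided 5% level and a linear model for continuous outcomes (Section V).

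**Assumed inputs.** Baseline-to-follow-up correlation r of 0.3, 0.5 or 0.7 among enrolled participants; follow-up SD set to 1; full follow-up, or 24 per arm if 20% are lost.

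**Formulas.** The unadjusted SE is sqrt(2/n), with n per arm. The ratio of adjusted to unadjusted SE is sqrt((1 − r²)(1 + 1/(N − 4))), where N = 2n and the second factor is the cost of estimating one slope. The half-width is SE × t, with N − 2 degrees of freedom unadjusted and N − 3 adjusted.

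**30 per arm.** SE = sqrt(2/30) = 0.2582 SD. With t(58) = 2.0017, the unadjusted half-width is 0.2582 × 2.0017 = 0.517 SD. The adjusted model uses t(57) = 2.0025.

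| r | SE ratio | SE change | Adjusted half-width (SD) |
|---|---|---|---|
| 0 | 1.0089 | +0.9% | 0.522 |
| 0.3 | 0.9624 | −3.8% | 0.498 |
| 0.5 | 0.8737 | −12.6% | 0.452 |
| 0.7 | 0.7205 | −28.0% | 0.373 |

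Break-even for the SE is where (1 − r²)(57/56) = 1, so r = sqrt(1/57) = 0.13.

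**24 per arm.** The unadjusted half-width is 0.581 SD. Adjusted, it is 0.561, 0.509 or 0.420 SD at r = 0.3, 0.5 or 0.7. At r = 0 the interval widens by about 1.2%.

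**Validity.** In simulation at 30 per arm (20,000 trials per setting, normal data), the unadjusted estimate averaged 0.497 to 0.502 for a true difference of 0.5 SD. Its type I error was 0.047 to 0.050, and that of the adjusted model 0.048 to 0.050. Both analyses are sound.

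**Effect of selection at entry.** Section b admits participants by symptom cut-offs: "Elevated symptoms of depression, anxiety, post-traumatic stress, or substance use disorder: At least one of the following". If r is a value that holds before selection, and everyone is elevated on a scale, restricting the baseline range lowers it to r√u / sqrt(1 − r² + r²u), where u is the ratio of baseline variance after selection to that before. The table takes a 0–27 scale cut at 10, with assumed pre-selection means and SDs and 30 per arm.

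| Mean, SD before selection | SE reduction at pre-selection r = 0.3 / 0.5 / 0.7 |
|---|---|
| 14, 6 | 1.4% / 6.4% / 16.7% |
| 11, 5.5 (u = 0.412) | 1.1% / 5.4% / 14.6% |
| 8, 6 | 0.6% / 3.8% / 11.2% |
| 6, 5 | 0.3% / 2.9% / 8.9% |

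The lower figures keep falling as the assumed mean falls, so none of these rows is a floor. Selection can also work the other way, because entry needs only one elevated domain out of four. With four right-skewed (exponential) scales, equal inter-scale correlation of 0.3 to 0.7 and 20% to 50% elevated on each, all assumed, u comes out at 1.05 to 1.38. The baseline range is then widened, not restricted, so the figures without range restriction are not a ceiling either.

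**The case against.** **An unadjusted analysis is a legitimate choice.** It is valid, and the plan promises no precision that it could fail to deliver. This stands, and it is why the point is an improvement and not a correction. A reader might infer that the missing covariate biases the symptom comparison or invalidates its P values. The documents do not support that: allocation is randomised 1:1, and the simulation shows no bias and correct type I error.

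**Baseline is already used through percentage reduction.** This is partly right and narrows the point to the severity-level models. It does not answer it. Dividing by baseline is not covariate adjustment, it leaves the severity model as it was, and it is undefined when a baseline score is zero. A zero can occur on a scale where the participant was not elevated. Nothing here shows that the adjusted score is generally the better outcome.

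**The model class could include covariates.** It could, but a plan that permits adjustment without naming it leaves the choice open until after the data are seen.

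**The size is unknown.** This stands. A reader might take the range-restricted and unrestricted figures as limits between which every scale must lie; the calculations above show that they are not. Only a 0–27 scale was worked through for range restriction, not PCL-5 or ASSIST.

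**The weight is low.** This also stands. The Assessments section makes the HIV outcomes the primary ones for the eventual full-scale trial and mental health the secondary ones, so the affected estimates are secondary in both studies.

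**The timing and source of the baseline scores are not stated outright.** That they precede randomisation, and that the eligibility scores form the baseline record, is inferred from the order of the sections from screening to randomization. The contents of the baseline assessment are not listed.

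**Conclusion.** The point holds as an optional gain in precision, at the lowest severity. The size rests on a correlation that the documents do not give. If the correlation among enrolled participants is 0.3 to 0.7, the standard error falls by about 4% to 28% at 30 per arm. If a scale's baseline range is strongly restricted by entry selection, the gain could be only a few per cent or less. Below a correlation of about 0.13 there is no gain, but the loss is then at most about 0.9% in interval width, or 1.2% at 24 per arm. The possible gain is much larger than the possible loss, and the data are collected anyway. No conclusion about bias, the pilot's primary outcomes or viral suppression follows.

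**What to change.** Add to Section V:

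> Each model for follow-up symptom severity (PHQ-9, GAD-7, PCL-5, ASSIST; at 4 months, and at 9 months where analysed) will include arm and, as a covariate, the participant's pre-randomisation (screening/baseline) score on the same scale; for ASSIST, the pre-randomisation value of the same score that is analysed as the outcome.

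The covariate is defined as the score itself so that a baseline of zero causes no difficulty. Two details should be settled at the same time, because the documents leave them open: which ASSIST score is the outcome, and how a missing baseline score is handled (it is not stated that every participant completes PCL-5).

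Leave percentage reduction, global improvement and the viral-load analysis unchanged. The cost is one sentence and one degree of freedom per model, with no new data collection.
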